### **9.3.2 Outcome Assessment**

#### **9.3.2.1 Primary Outcome**

Major congenital malformations will be defined overall and by each malformation group using ICD-10-CM codes from the National Birth Defects Prevention Network (NBDPN) birth defects descriptions for the NBDPN core and recommended conditions including:

Central Nervous System (eg, anencephalus, spina bifida without anencephalus, encephalocele)

Eye (eg, anophthalmia/microphthalmia)

Ear (eg, anotia/microtia)

Cardiovascular (eg, common truncus, transposition of great arteries, tetralogy of fallot, ventricular septal defect, atrial septal defect, atrioventricular septal defect, pulmonary valve atresia and stenosis, tricuspid valve atresia and stenosis, Ebstein anomaly, aortic valve stenosis, hypoplastic left heart syndrome)

Orofacial (eg, cleft palate with and without cleft lip, choanal atresia)

Gastrointestinal (eg, esophageal atresia/tracheoesophageal fistula, rectal and large intestinal atresia/stenosis, small intestinal atresia/stenosis)

Genitourinary (eg, renal agenesis/hypoplasia, bladder exstrophy, hypospadias)

Musculoskeletal (eg, clubfoot, limb deficiencies, gastroschisis, omphalocele, diaphragmatic hernia)

See [Appendix D](#) for a full list of conditions and ICD-10 diagnosis codes

([https://www.nbdpn.org/docs/Appendix\\_3\\_1\\_BirthDefectsDescriptions2015\\_2016DEC14.pdf](https://www.nbdpn.org/docs/Appendix_3_1_BirthDefectsDescriptions2015_2016DEC14.pdf)). Outcomes that are not associated with drug exposure, such as chromosomal abnormalities, genetic syndromes, prematurity-related defects, and positional effects will be excluded from our definition of major congenital malformations. When linked medical records are available for validation studies conducted in the HealthCore Integrated Research Database, we will collect additional information on reasons (ie, chromosomal abnormality) for non-live births, including spontaneous abortions, where available.

#### **9.3.2.2 Secondary outcomes**

Spontaneous abortion is defined as loss of the embryo or fetus between conception and the point at which the death would be considered a stillbirth, at week 20 or later ([Likis et al, 2013](#)). In the MarketScan CCE database and the HIRD, spontaneous abortion will be identified through ICD-10-CM diagnostic codes and procedure codes (see [Appendix E](#) for codes).

Stillbirth is generally defined as intrauterine fetal death on or after the 20th week of gestation, of a fetus weighing 350 grams or more ([Likis et al, 2013](#)). Although the date of fetal death may not be known, stillbirth is more likely than spontaneous

abortion to be medically attended, and will be identified through ICD-10-CM diagnostic codes and procedure codes in the MarketScan CCE database and the HIRD (see [Appendix F](#) for codes).

Small-for-gestational age in live born (LB) infants, defined as birth weight 10th percentile, will be identified using ICD-10-CM codes in the MarketScan CCE database and the HIRD (see [Appendix G](#) for codes).

### 9.3.3 Covariate Assessment

Study cohorts will be described according to baseline covariates. Demographic attributes will be determined on the cohort entry date while others will be assessed during the baseline period, unless otherwise specified. All covariate information will be ascertained through inpatient and/or outpatient claims for diagnoses and procedures, and through pharmacy claims utilizing ICD-10 CM for diagnoses; ICD-10 PCS, CPT, or HCPCS codes for procedures; and GPI or NDC codes for dispensings. Additional details will be provided in the Statistical Analysis Plan (SAP) and the Medical Record Plan (MRP).

Covariates to be assessed include the following:

- Maternal age at estimated LMP (in years)

- Maternal race, if available

- Calendar year at estimated LMP

- Geographic region of health plan

- Migraine characteristics (eg, migraine with aura, chronic migraine)

- Comorbid conditions at baseline (eg, chronic hypertension, hyperlipidemia, diabetes, polycystic ovarian syndrome, hypothyroidism, hyperthyroidism, depression, anxiety, epilepsy), identified through ICD-10-CM diagnosis codes

- Medications in the baseline period (eg, acute and preventive migraine treatments, other treatments not for migraine, suspected teratogenic medications), identified through NDC codes or HCPCS codes

- Adverse events during pregnancy (eg, pre-eclampsia, gestational diabetes), identified through ICD-10-CM diagnosis codes

- Concomitant medications with claims after or a days supply that overlaps the LMP date and by trimester during the pregnancy (eg, acute migraine treatments, other treatments not for migraine, suspected teratogenic medications), identified through NDC codes or HCPCS codes

- History of obstetric outcomes (eg, prior pregnancies, multiple gestation, outcomes of prior pregnancies including spontaneous abortions) using all available history

- Use of prenatal testing

- Resource utilization (eg, number of prenatal visits, types of providers visited, emergency department visits)

- Body mass index, if available

- Alcohol, tobacco, and substance abuse, if available

Exposure to infections during pregnancy, if available  
 Previous history of congenital malformations, if available

### 9.3.4 Validity and Reliability

#### *Identification of pregnancy and timing of exposure assessment during pregnancy*

Administrative databases can be useful in the assessment of prenatal drug exposure, and estimation of the LMP is necessary to classify exposure. Incorrect gestational age information can lead to misclassification of medication exposure during specific periods of pregnancy. Since there are no definitive diagnosis codes that clearly indicate the last menstrual period, pregnancy duration, or gestational age, diagnosis and other procedure codes have been recommended and utilized to determine the LMP. Approaches to arrive at the LMP in patients with live birth outcomes has been studied in administrative claims data using ICD-9 coding and have been shown to accurately identify most of these pregnancies (Ailes EC et al, 2016; Margulis AV et al, 2015; Naleway et al, 2013); however, there is no validated approach for pregnancies ending in non-live outcomes, and no studies have examined the impact of changes in ICD-10 coding

We previously tested the feasibility of three approaches (see Appendix B for details) in the MarketScan CCE databases to identify the LMP among pregnancies resulting in fetal death (Hornbrook et al, 2007; Kharbanda et al, 2012; Glaxo SmithKline 2017).

Results from the feasibility analysis estimating the mean and median gestational age (in weeks) using the three different methods are presented in Table 1. We propose to use an approach like the one described by Hornbrook et al, 2007 which uses outcome-specific estimates of gestational age developed by the Centers for Disease Control and Prevention. The percent agreement between the claims-based algorithm and medical record ranged from 87.5 to 96.3% for non-live birth outcomes (eg, therapeutic abortion, spontaneous abortion, and stillbirth), and from 86.6% to 100% for dates of these non-live birth outcomes.

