### 9.3.1.1 Timing of Exposure Assessment

#### *Estimated date of last menstrual period (LMP)*

For the calculation of LMP, the following approach will be implemented for all types of pregnancy outcomes, including spontaneous abortion, stillbirth, and live birth.

For the identified end of pregnancy episode, LMP estimation will be based on identifying certain pregnancy-related diagnosis and/or procedure codes and in particular Z3A.® (Z3A), an ICD-10-CM set of codes that indicate weeks of gestation of pregnancy, with the last 2 characters corresponding to specific weeks of gestation. Even though the Z3A codes are not billable codes, insurance providers, *such as Anthem Blue Cross Blue Shield*, are requiring the reporting of Z3A codes for childbirth delivery claims and especially for early elective procedures ([Jamal-Allial et al, 2019](#)). The Z3A code category may serve to more accurately estimate the timing of the pregnancy using administrative claims data. Z3A codes have to be reported alongside the primary pregnancy/delivery code of interest. Because these codes are specific to each week of pregnancy, LMP estimation will be based on the indicated number of weeks of gestation for that reported Z3A code, and an approximate mid-point will be applied, ie, 4 days to each period ([Suarez, 2018](#)).

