When Z3A codes are not available, weeks of gestation for LMP estimation will be inferred using an algorithm that is informed by algorithms reported in the literature and refined clinical input will be utilized to estimate the corresponding EDC ([Hornbrook et al, 2007](#); [Margulis et al, 2013](#); [Margulis et al, 2015](#); [Mines et al, 2014](#); [Ailes et al, 2016](#)). The algorithms reported in the literature assume different lengths of gestation for the different pregnancy outcomes, such as full-term singleton births (40-39 weeks), multiples births (36-40 weeks), stillbirths (20-38 weeks), spontaneous abortions ( 20 weeks), and ectopic pregnancies (8 weeks). Recognizing these algorithms may over- or underestimate the true gestational age, other codes that indicate weeks of gestation (eg, HCPCS S2260, *induced abortion, 17-24 weeks*) or the trimester of pregnancy (eg, ICD-10 O09.612, *supervision of young primigravida, second trimester*) will be explored. For codes that are associated with a range of gestational age, an approximate mid-point of gestational weeks 4 days will be assigned based on the reported pregnancy-term code, eg, HCPCS S2260: *induced abortion, 17 to 24 weeks*, so the assigned GA is 20.5 weeks 4 days will be used for EDC estimation. Additional details on validation will be provided in the Statistical Analysis Plan (SAP) and the Medical Record Plan (MRP).

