### **9.8.1 Internal Validity of Study Design**

#### **9.8.1.1 Measurement Error(s)/Misclassification(s)**

The algorithm used for identification of pregnancy episodes and outcomes for pregnancies that end in live births is very robust (99% agreement between algorithm and chart review). However, ascertainment of LMP and gestational age for pregnancies ending in spontaneous abortion or stillbirth is challenging. We will use a previously published method, such as Hornbrook et. Al. to estimate gestational age and LMP.

As with any observational study conducted within the context of an insurance claims database, drug exposure and timing of exposure is never entirely certain. Although there is evidence in the claims of patients receiving a prescription dispensing at an outpatient pharmacy, we are unable to verify that patients actually used the medication.

Conversely, pregnant patients may take pills during pregnancy that were obtained from a prescription written and dispensed prior to the conception date. In addition, the prescription database lacks information on non-reimbursable (over-the-counter) analgesics, medication dispensed during hospital admissions, or obtained from the doctor's office as samples.

The completeness and/or sensitivity of some of the covariates of interest, such as body mass index, alcohol, tobacco and substance abuse, and previous history of congenital malformations, may be low, and residual confounding due to these characteristics may still be present.

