## Appendix B. Feasibility Assessment and Comparison of Methods for Timing of Exposure Assessment During Pregnancy

Administrative databases can be useful in the assessment of prenatal drug exposure, and estimation of the LMP date is necessary to classify exposure. Incorrect gestational age information can lead to misclassification of medication exposure during specific periods of pregnancy. Since there are no definitive diagnosis codes that clearly indicate the last menstrual period, pregnancy duration, or gestational age, diagnosis and other procedure codes have been recommended and utilized to determine the last menstrual period (LMP). Approaches to arrive at the LMP in patients with live birth outcomes have been thoroughly studied in administrative claims data and have been shown to accurately identify most of these pregnancies ([Ailes EC et al, 2016](#); [Margulis AV et al, 2015](#); [Naleway et al, 2013](#)); however, there is no validated approach for pregnancies ending in non-live outcomes.

We previously tested the feasibility of three approaches in the MarketScan CCE databases to identify the LMP among pregnancies resulting in fetal death ([Hornbrook et al, 2007](#); [Kharbanda et al, 2012](#); [Glaxo SmithKline 2017](#)). To test the first approach ([Hornbrook et al, 2007](#)), we assigned outcome-specific gestational age estimates based on national averages from the literature ([Martin et al, 2003](#); [Copper et al, 1994](#)). Assigning a fixed estimate (eg, patients with stillbirths were assigned a gestational period of 28 weeks) yielded no variability in the gestational age assignment among patients with identical outcomes, which did not accurately reflect the true date of the LMP. However, the approach provided solutions to address pregnancy durations that were incompatible with the respective pregnancy outcomes, overlapping pregnancy episodes, and subsequent pregnancy episodes, which are described in more detail in [Section 9.3.1.1](#)).

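### For pregnancy losses with no gestational-age code, the protocol proposes an LMP method that its own Appendix B found inaccurate, so exposure windows may be misplaced by about 2 to 6 weeks

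*Protocol*

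**What the plan says.** Section 9.3.1.1 sets one order of steps for every outcome. First, "LMP estimation will be based on the indicated number of weeks of gestation for that reported Z3A code". Some insurers, it adds, "are requiring the reporting of Z3A codes for childbirth delivery claims and especially for early elective procedures". Second, "When Z3A codes are not available, weeks of gestation for LMP estimation will be inferred using an algorithm" drawn from several published algorithms and clinical input. These algorithms assume a length of gestation by outcome, including live births; the stillbirth range given is 20 to 38 weeks. The section then adds a hedge: "Recognizing these algorithms may over- or underestimate the true gestational age, other codes that indicate weeks of gestation" or trimester are to be explored.

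For losses, section 9.3.4 says that no validated approach exists and proposes one like Method 1 of the feasibility work, "which uses outcome-specific estimates of gestational age developed by the Centers for Disease Control and Prevention". Section 9.8.1.1 repeats this for spontaneous abortion and stillbirth: "We will use a previously published method, such as Hornbrook et. Al. to estimate gestational age and LMP".

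Appendix B describes the test of that method in MarketScan. Giving one fixed value per outcome (28 weeks for every stillbirth) "yielded no variability in the gestational age assignment among patients with identical outcomes, which did not accurately reflect the true date of the LMP". The merit it reports is the handling of incompatible, overlapping and subsequent episodes, not accuracy of the LMP.

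Section 9.3.1 counts a woman as exposed if she has a fill in the 112 days before the LMP or during pregnancy. It starts the second trimester at day 91 and the third at day 181 after the LMP.

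**The concern.** The LMP drives exposure status, the trimester categories, the baseline period and the matching on LMP date and gestational age. Section 9.3.4 itself warns that a wrong gestational age misclassifies exposure. If losses are dated less accurately than live births, the misclassification is related to the outcome, and the odds ratios for spontaneous abortion and stillbirth can be biased. With too short an assigned gestation, the window opens too late and exposed losses are counted as unexposed. In a safety study that hides harm. A single fixed value also carries none of the dating uncertainty into the confidence intervals.

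**Working it through.** **Plan's own figures.** Table 1 comes from patient-level data and cannot be regenerated, but it can be checked for consistency. For a given mean and range the largest possible SD is sqrt((max - mean)(mean - min)).

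- Spontaneous abortion: sqrt(0.1 x 9.8) = 0.99, stated SD 0.7.
- Stillbirth: sqrt(0.2 x 21.9) = 2.09, stated SD 1.7.

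Both rows are feasible. In both the median equals the maximum (10.0 and 28.0 weeks), which fits a fixed value shortened in a minority of episodes and agrees with the 28 weeks in Appendix B.

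**Shift against the other methods (Table 1).** Shift = other method minus Method 1, times 7 for days.

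| Outcome | Comparison | Means | Medians |
|---|---|---|---|
| Spontaneous abortion | Method 2 | 14.4 - 9.9 = +4.5 wk (31.5 d) | 13.1 - 10.0 = +3.1 wk |
| Spontaneous abortion | Method 3 | 12.1 - 9.9 = +2.2 wk (15.4 d) | 12.3 - 10.0 = +2.3 wk |
| Stillbirth | Method 2 | 27.1 - 27.8 = -0.7 wk (-4.9 d) | 26.0 - 28.0 = -2.0 wk |
| Stillbirth | Method 3 | 33.4 - 27.8 = +5.6 wk (39.2 d) | 33.7 - 28.0 = +5.7 wk |

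As a share of the 112-day window, the mean shifts are 14% to 28% for spontaneous abortion and 4% to 35% for stillbirth.

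**Trimester categories.** A spontaneous abortion dated at 10 weeks ends on day 70. The second trimester starts on day 91, so it can never be classed as second-trimester exposed, although the outcome runs to week 20. A stillbirth dated at 28 weeks ends on day 196, so it always has 16 third-trimester days (181 to 196), whatever its true length.

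**Exposed or not.** The window ends on the claim date, so only its start moves. Assume that the last fill is uniform over the true window, that exposure is uncommon, that live births are dated correctly, and that a share u of losses has no code. With true gestation t weeks and assigned gestation a weeks, the share of exposed losses missed is u x 7(t - a)/(112 + 7t), and a true odds ratio of 1.0 reads about one minus that share.

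- Spontaneous abortion, a = 10, t = 12.1: 14.7/196.7 = 0.075. Odds ratio 0.925 at u = 1 and 0.981 at u = 0.25.
- Spontaneous abortion, a = 10, t = 14.4: 30.8/212.8 = 0.145. Odds ratio 0.855 at u = 1 and 0.964 at u = 0.25.
- Stillbirth, a = 28, t = 27.1: -6.3/301.7 = -0.021. Odds ratio 1.021 at u = 1 and 1.005 at u = 0.25.
- Stillbirth, a = 28, t = 33.4: 37.8/345.8 = 0.109. Odds ratio 0.891 at u = 1 and 0.973 at u = 0.25.

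**Live births under the same fallback.** If an uncoded singleton is assumed to be 39.5 weeks (midpoint of the stated 39 to 40), a birth at 34 weeks is misdated by 5.5 weeks, at 36 weeks by 3.5 and at 41 weeks by -1.5.

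**The case against.** The case for the plan has several sound parts.

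- **The method is not strictly fixed.** Sections 9.3.4 and 9.8.1.1 name the published method only as a model, and section 9.3.1.1 gives ranges and mentions other codes. A reader might infer that the plan sets 10 and 28 weeks. It does not: those are the values in the feasibility test. It also gives no other rule for uncoded losses, and looking at other codes is left to exploration.
- **Live births are not immune.** A reader might infer that only losses are misdated. The fallback covers all outcomes, and uncoded preterm births are misdated by weeks too. The live-birth accuracy in section 9.3.4 is for most pregnancies and under ICD-9. What stands is a difference of degree.
- **Stillbirths are deliveries.** Appendix F identifies them largely by delivery-outcome codes, so many may carry a Z3A code. The problem probably weighs more on spontaneous abortion.
- **The 5.9-week stillbirth in Table 1** looks like a flaw of the fixed value, but the same minimum appears under all three methods.
- **Shares of misclassified exposure depend on the assumptions.** With stillbirths uniform over 20 to 38 weeks, the mean absolute error against 28 is (8^2/2 + 10^2/2)/18 = 4.56 weeks. If fills are spread over 168 days before to 56 days after the LMP (224 days), exposure is wrong in 4.56 x 7/224 = 14.2%. Extending the spread to day 203 (371 days) gives 8.6%. Neither is a forecast.
- **Mitigation is planned:** LMP validation in HIRD records, analyses varying exposure timing, and quantitative bias analysis. But validation is in one database with about 60% record retrieval, the bias analysis is exploratory, and no rule changes the dating of losses in response.

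The agreement figures in section 9.3.4 (87.5% to 96.3%, and 86.6% to 100%) do not answer the point. They concern the type and date of the non-live outcome and are not stated to cover gestational age or LMP.

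**Conclusion.** The point holds in a limited form. The protocol proposes for losses an approach whose tested version its own appendix calls inaccurate for the LMP, and it does not explain the choice. Applied as tested, the window start and the trimester categories may be off by about 2 to 6 weeks in uncoded losses, probably more than in most live births. For stillbirth the evidence is mixed: the mean gap to Method 2 is only -0.7 weeks. Table 1 shows disagreement between methods, not error against a standard, and Appendix B criticises Method 2 as well.

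The trimester categories suffer most. For ever-exposed status the bias is modest unless most losses are uncoded: about 0.96 to 0.98 for a true spontaneous abortion odds ratio of 1.0 at 25% uncoded, and about 0.86 to 0.93 if all are. Both rest on the uniform-fill assumption and on an uncoded share that the protocol does not give. The affected outcomes are secondary and their comparisons are conditional on sample size, so this is a change that should be made rather than a fatal flaw.

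**What to change.** - Reconcile sections 9.3.1.1, 9.3.4 and 9.8.1.1 with Appendix B, so that one stated rule dates uncoded losses.
- Make the use of other week-specific or trimester codes a rule instead of something to explore.
- Where none exists, assign gestational age from the distribution in Z3A-coded losses of the same outcome in the same database, bounded below 20 weeks for spontaneous abortion and at 20 weeks or more for stillbirth. Write an exception to the no-imputation rule in section 9.6.2.2. Repeated draws, which would carry the uncertainty into the intervals, are optional; statisticians could differ on them.
- Report the share of losses and of live births without a code, by cohort and database.
- Add a sensitivity analysis limited to losses with a Z3A or other week-specific code.

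This needs no new data. The cost is a little programming, some loss of precision, and an assumption that coded and uncoded losses have similar gestational ages. The planned LMP validation in the HIRD can check that assumption.

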**Table 1. Feasibility Assessment to Estimate Gestational age (in weeks) Based on Three Different Methods**

	Method 1 – using gestational age estimates based on national averages from literature (Hornbrook et al, 2007)		Method 2 – using prenatal screening claims prior to pregnancy outcome date (Kharbanda et al, 2012)		Method 3 - triangular distribution to estimate pregnancy episode duration, (Glaxo SmithKline 2017)	
	Estimated gestational age, in weeks					
Pregnancy outcome	Mean (SD)	Median (Range)	Mean (SD)	Median (Range)	Mean (SD)	Median (Range)

Spontaneous Abortion	9.9 (0.7)	10.0 (0.1-10.0)	14.4 (4.5)	13.1 (4.1-30.0)	12.1 (1.2)	12.3 (0.1-13.7)
Stillborn	27.8 (1.7)	28.0 (5.9-28.0)	27.1 (9.4)	26.0 (5.9-48.0)	33.4 (2.4)	33.7 (5.9-35.6)

### *Mother-infant linkage*

Algorithms for linking mothers and their infants in administrative data have been validated in the MarketScan CCE Databases and other claims databases ([Hanley and Mintzes, 2014](#); [Kharbanda et al, 2012](#); [Li et al, 2013](#); [Naleway et al, 2013](#); [Palmsten et al, 2013](#)). Linking mother and baby claims is necessary to obtain information on medication exposure during pregnancy, since the infant has no individual pharmacy claims until after birth. Insurance identification numbers typically consist of an encrypted Social Security Number for the primary insured person, plus an additional number for each dependent covered under the primary insured's plan. We will be using the same methods to link mothers and infants as was developed by the FDA Sentinel pregnancy module ([Kawai et al, 2017](#)).

Since HealthCore, Inc.-via Anthem, Inc. data-is a major contributor to the Sentinel Collaboration, as of March 2020, HealthCore created a linked Mothers and Infants Table in their HealthCore Integrated Research Environment (HIRE) system which can be used for pregnancy and infants' research. As of March 2019, there are 1.7 million mothers, 3 million infants, and 1.2 linked mothers and infants. HealthCore follows a multi-step process provided by the FDA Sentinel program for creating such tables. The first part is creating Mothers and Infants Table through the Sentinel Modular programs. This is followed by linking the mothers and infants through SubscriberID within DCC and, finally, HealthCore performs quality assurance programming to verify that mothers and infants were correctly linked. The HIRD currently includes around 800,000 mother-infant pairs. In 2017, the HIRD included 11,704 pregnant women with migraine.

